**Table 5: Pre-specified Dose/Schedule Modifications for Adverse Events Related to Study Drug**

	Dose Level	Selinexor Dosing
	1	100 mg BIW (total dose of 200 mg per week)
Starting Dose	0	80 mg BIW (total of 160 mg per week)
Dose Reductions	-1	60 mg BIW (120 mg total per week)
	-2	100 mg total per week: 100 mg one day OR divided as 60 mg and 40 mg on separate days
	-3	80 mg total per week: 80 mg one day OR divided as 40 mg per day on 2 days
	-4	60 mg total per week: 60 mg one day OR divided as 40 mg one day and 20 mg on another day
	-5	40 mg total per week: 40 mg one day OR divided as 20 mg per day on separate days

Abbreviation: BIW = twice weekly

**Table 6: Supportive Care and Dose Adjustment Guidelines**

**Please note the following recommendations:**

- After consultation with the Medical Monitor and at the discretion of the Investigator, selinexor dosing may be maintained for all hematological or non-hematological AEs that are NOT related to selinexor.
- For all selinexor-related AEs, if the prescribed dose reductions/interruptions in [Table 8](#) result in a stabilization of  $\geq 4$  weeks, a re-escalation may be considered after approval from the Medical Monitor.

Toxicity and Intensity	Selinexor Dose Modification
Fatigue (common)	
Grade 1 or Grade 2 lasting $\leq 7$ days	Maintain dose. Rule out other causes of fatigue, particularly dehydration and anemia. If found to be anemic, consider transfusing for hemoglobin $< 8$ g/dL. Institute supportive care medications per institutional guidelines and NCCN CPGO.  Patients with significant fatigue after several doses of selinexor may have an ongoing anti-tumor response. If fatigue is significant, consider assessment of tumor response as part of the patient's evaluation.
Grade 2 lasting $> 7$ days or Grade 3	Rule out other causes of fatigue, particularly dehydration and anemia. If found to be anemic, consider transfusing for hemoglobin $< 8$ g/dL. Institute supportive care medications per institutional guidelines and NCCN CPGO.  Interrupt selinexor dosing until resolved to Grade 1 or baseline.  For first occurrence, restart selinexor at current dose.  For $\geq$ second occurrence, reduce selinexor by 1 dose level when resuming selinexor. ( Table 5 ).  Patients with significant fatigue after several doses of selinexor may have an ongoing anti-tumor response. If fatigue is significant, consider assessment of tumor response as part of the patient's evaluation.

Toxicity and Intensity	Selinexor Dose Modification
Anorexia or Weight Loss	
Grade 1 anorexia Grade 1 weight loss Grade 2 anorexia	Maintain dose. Rule out other causes and consider a repeat nutritional consultation and nutritional supplements (e.g., Ensure®, Boost®, etc.). Institute supportive care medications per institutional guidelines and NCCN CPGO.
Grade 2 weight loss Grade ≥ 3 anorexia or weight loss	Rule out other causes and consider a repeat nutritional consultation and nutritional supplements (e.g., Ensure®, Boost®, etc.). Institute supportive care medications per institutional guidelines and NCCN CPGO.  Interrupt dosing with selinexor until improves to Grade 1 or baseline and weight stabilizes, then reduce selinexor by 1 dose level when resuming selinexor (Table 5).  Consult Medical Monitor to discuss persistent or ≥ second occurrence of weight loss after stabilization.
Nausea, Acute (common)	
Grade 1 or 2 (If intolerable or persistent Grade 2 not responsive to supportive care, follow guidelines for Grade 3 below)	Maintain dose. Rule out other causes of nausea. Implement additional anti-nausea medications to supplement the protocol-required 5-HT3 antagonists using institutional guidelines and NCCN CPGO.
Grade 3	Rule out other causes of nausea. Implement additional anti-nausea medications to supplement the protocol-required 5-HT3 antagonists using institutional guidelines and NCCN CPGO.  Interrupt selinexor dosing until resolved to Grade ≤ 2 or baseline and restart selinexor at 1 dose level lower (Table 5).
Hyponatremia (common)	
Grade 1 (sodium levels < Normal to 130 mmol/L)	Maintain dose. Rule out other causes including drug (e.g., diuretic) effects. Be certain that reported sodium level is corrected for concurrent hyperglycemia (serum glucose > 150 mg/dL).  Treat hyponatremia per institutional guidelines including dietary review. Consider addition of salt tablets to patient's diet.
Grade 3 with sodium levels 120 to <130 mmol/L without symptoms	Correct for hyperglycemia as outlined under Grade 1. Treat hyponatremia per institutional guidelines. If (corrected) sodium is Grade ≤ 3 and continues to be asymptomatic, then patient may continue current dosing provided that intravenous saline and/or salt tablets (1-3 times daily) are provided.  If Grade 3 is persistent or worsens or does not respond to treatment, hold selinexor until resolved to Grade 1 or baseline and reduce selinexor by 1 dose level.
Grade 3 with sodium levels 120 to <130 mmol/L with symptoms or Grade 4 (<120 mmol/L)	Correct for hyperglycemia as outlined under Grade 1. Treat hyponatremia per institutional guidelines. Delay/hold selinexor until resolved to Grade 1 or baseline then reduce selinexor dose by 1 level (Table 5).

Toxicity and Intensity	Selinexor Dose Modification
Diarrhea (common)	
Grade 1	Maintain selinexor dosing. Rule out other causes including drug effects. Initiate anti-diarrheal treatment per institutional guidelines.
Grade 2	Rule out other causes including drug effects. Treat per institutional guidelines. Interrupt selinexor until resolved to Grade 1 or baseline.  For first occurrence, restart selinexor at current dose. For $\geq$ second occurrence, reduce selinexor by 1 dose level (Table 5).
Grade 3 or 4	Delay selinexor until resolved to Grade 1 and the patient is clinically stable, then reduce selinexor dose by 1 dose level (Table 5).
Thrombocytopenia	
Grade 1 or 2	Maintain dose. Rule out other causes including drug effects.
Grade 3 Thrombocytopenia without bleeding	
Consider platelet growth factors per institutional guidelines.
 
Do not interrupt/hold selinexor but dose reduce as below:
 
For patients on 80 mg BIW (starting dose, Dose Level 0):            Do not hold selinexor.            Dose reduce to 100 mg total dose per week (Dose Level -2) but dosed at QW schedule until recovery to Grade <math>\leq</math> 2 or baseline and then may resume the total weekly dose scheduled as BIW (100 mg divided as 60 mg and 40 mg).
 
For patients on all other dose levels:            Do not hold selinexor.            Dose reduce by one dose level but dose the patient at the total weekly dose as QW until further recovery to Grade <math>\leq</math> 2 or baseline and then resume the total weekly dose scheduled as BIW.
 
For example, patients who were on dose level -2 (100 mg QW or divided as 60 mg and 40 mg) and need to de-escalate to dose level -3 (80 mg total per week), should be dosed at 80 mg QW until platelets recover to Grade <math>\leq</math> 2 or baseline and then may resume the same total weekly dose of 80 mg total as a divided schedule of 40 mg BIW.
 
*For <math>\geq</math> second occurrence or worsening thrombocytopenia despite measures above: Hold selinexor until recovery to Grade <math>\leq</math> 2 or baseline and resume at 1 dose level lower dosed at QW schedule.
 
CCI  

Toxicity and Intensity	Selinexor Dose Modification

Grade 4                      Thrombocytopenia without bleeding
	
Strongly consider platelet growth factors and transfuse per clinical practice/institutional guidelines.
 
Delay or hold selinexor dosing until platelets recover to Grade <math>\leq 3</math> and see below:
 
For patients on 80 mg BIW (starting dose, Dose Level 0):                      Hold selinexor until recovery to Grade <math>\leq 3</math>, then dose reduce to 100 mg total dose per week (Dose Level -2) but dosed at QW schedule until further recovery to Grade <math>\leq 2</math> or baseline and then may resume the total weekly dose scheduled as BIW (100 mg divided as 60 mg and 40 mg).
 
For patients on all other dose levels:                      Hold selinexor until recovery to Grade <math>\leq 3</math>, then dose reduce by one dose level but dose the patient at the total weekly dose at the QW schedule until further recovery to Grade <math>\leq 2</math> or baseline and then may resume the total weekly dose scheduled as BIW. For example, patients who were on dose level -2 (100 mg QW or divided as 60 mg and 40 mg) and need to de-escalate to dose level -3 (80 mg total per week), should be dosed at 80 mg QW until platelets recover to Grade <math>\leq 2</math> or baseline and then may resume the same total weekly dose of 80 mg total as a divided schedule of 40 mg BIW.
 
*For <math>\geq</math> second occurrence or worsening thrombocytopenia despite measures above: Hold selinexor until recovery to Grade <math>\leq 2</math> or baseline and resume at 1 dose level lower dosed at QW schedule.
 
**If the occurrence falls on Day 1 of a cycle, delay the start of the cycle and check platelet counts weekly until recovery to Grade <math>\leq 3</math> and follow the guidelines above.
 
CCI  


Grade <math>\geq 3</math>                      Thrombocytopenia with bleeding
	
Delay/hold dosing until the bleeding has stopped and the patient is clinically stable. When resuming selinexor, see below:
 
For patients on 80 mg BIW (starting dose, Dose Level 0):                      Upon recovery to Grade <math>\leq 2</math> or baseline, dose reduce to 100 mg total dose per week (Dose Level -2) but dosed at the QW schedule until further recovery to Grade <math>\leq 1</math> and then may resume the total weekly dose scheduled as BIW (100 mg divided as 60 mg and 40 mg).
 
For patients on all other dose levels:                      Upon recovery to Grade <math>\leq 2</math> or baseline, dose reduce by one dose level, but dose the patient at the total weekly dose at the QW schedule until further recovery to Grade <math>\leq 1</math> or baseline and then may resume the total weekly dose scheduled as BIW.
 
For example, patients who were on dose level -2 (100 mg QW or divided as 60 mg and 40 mg) and need to de-escalate to dose level -3 (80 mg total per week), should be dosed at 80 mg QW until platelets recover to Grade <math>\leq 1</math> or baseline and then may resume the same total weekly dose of 80 mg total as a divided schedule of 40 mg BIW.

Toxicity and Intensity	Selinexor Dose Modification
	
**If the occurrence falls on Day 1 of a cycle, delay the start of the cycle and check platelet counts weekly until the bleeding has stopped, recovery to Grade <math>\leq 3</math> and the patient is clinically stable and follow the guidelines above.
 
CCI [REDACTED]

Neutropenia	
Grade 3 or 4 Neutropenia with fever (febrile neutropenia) or without fever	
Institute colony stimulating factors and prophylactic antibiotics as clinically indicated per institutional guidelines. Interrupt selinexor and check neutrophils weekly until recovery to Grade <math>\leq 2</math> or baseline and without fever (if febrile) and the patient is clinically stable. Reduce selinexor by 1 dose level when resuming.
 
If the occurrence falls on Day 1 of a cycle, delay start of a cycle and check neutrophils weekly until recovery to Grade <math>\leq 2</math> or baseline and without fever (if febrile) and the patient is clinically stable. Reduce selinexor by 1 dose level when resuming.

Anemia	
Treat per institutional guidelines including blood transfusions and/or erythropoietins. Consider transfusing for any hemoglobin $< 8$ g/dL. If possible, maintain selinexor dose as long as patient is clinically stable, but if dose reduction or interruption is desired, discuss with the Medical Monitor.	
Other Selinexor-Related Adverse Events	
Grade 1 or 2	Maintain dose. Rule out other causes. Initiate treatment and/or standard supportive care per institutional guidelines.
Grade 3 or 4	
Rule out other causes. Interrupt selinexor until recovery to Grade <math>\leq 2</math> or baseline and reduce selinexor by 1 dose level.
 
Isolated values of Grade <math>\geq 3</math> alkaline phosphatase do NOT require dose interruption. Determination of liver versus bone etiology should be made, and evaluation of gamma-glutamyl transferase, 5'-nucleotidase, or other liver enzymes should be performed.

Abbreviations: 5-HT3 = 5-hydroxytryptamine; BIW = twice weekly; NCCN CPGO = National Comprehensive Cancer Network Clinical Practice Guidelines in Oncology; QW = once weekly

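### The visible thrombocytopenia rules in Table 6 send a patient escalated to 100 mg twice weekly to a single 160 mg dose, above the protocol's 70 mg/m² cap at any BSA below 2.29 m²

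*Protocol*

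**What the plan says.** **Dose levels (Protocol Table 5).** Dose Level 1 is "100 mg BIW (total dose of 200 mg per week" and Dose Level 0, the starting dose, is "80 mg BIW (total of 160 mg per week". Dose Level -1 is 60 mg twice weekly. A one-day option first appears at Dose Level -2, as 100 mg. No level lists a larger one-day dose.

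**Thrombocytopenia rows (Protocol Table 6).** All three visible rows use the same two branches.

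- Patients on 80 mg twice weekly skip a level. In the Grade 3 row without bleeding: "Dose reduce to 100 mg total dose per week (Dose Level -2) but dosed at QW schedule".
- Every other dose level drops one step and takes the week's total in one dose. Grade 3 without bleeding: "Dose reduce by one dose level but dose the patient at the total weekly dose as QW until further recovery". Grade 4 without bleeding: "then dose reduce by one dose level but dose the patient at the total weekly dose at the QW schedule". Grade 3 or higher with bleeding: "dose reduce by one dose level, but dose the patient at the total weekly dose at the QW schedule until further recovery".

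The Grade 3 row without bleeding also says "Do not interrupt/hold selinexor but dose reduce as below". The only worked example in these rows is the step from Dose Level -2 to -3.

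**The cap.** Protocol Sections 5.1, 7.1, 11.1.3 and 11.1.5.5 say the dose may in no case exceed 70 mg/m². Footnote 3 of Protocol Table 1, repeated in SAP Table 7-1, says no patient may receive more than that.

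**Escalation.** Section 7.1 allows 100 mg in select patients who are tolerating treatment well, after at least two cycles and in consultation with the Medical Monitor. Section 11.1.1 asks for Medical Monitor discussion before any dose modification.

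**The concern.** Dose Level 1 is not the starting dose, so on the visible wording it can only fall in the residual branch. That branch combines a one-level reduction with giving the whole weekly total at once. From Dose Level 1 the result is 160 mg in a single administration, a dose the protocol elsewhere prohibits for most body sizes.

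The patients concerned have low platelets when the rule applies. In the Grade 3 row the drug is not held, so the instruction operates during Grade 3 thrombocytopenia. In the Grade 4 row it operates once platelets recover to Grade 3 or better. In the bleeding row it operates after bleeding has stopped and platelets reach Grade 2 or better, or baseline. Thrombocytopenia is common with this regimen: Protocol Section 4.3.1.4 reports 51% treatment-related Grade 3/4 events (N = 92). Escalated patients are selected for good tolerance, so their rate may be lower.

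The step is labelled a reduction. The protocol ties BSA calculation to Screening and to dose increases, so nothing in the visible text prompts a fresh check against the cap.

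**Working it through.** **1. Is the cap per dose or per week?** Section 5.1 bars escalation to 100 mg below a BSA of 1.4 m² because the cap would be exceeded. Reproducing that figure: 100 mg ÷ 70 mg/m² = 1.429 m², which is 1.4 to one decimal. The protocol therefore applies the cap to each administered dose. A weekly cap would rule out the starting dose itself below 160/70 = 2.29 m², which cannot be meant.

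**2. What does the residual branch give?** Weekly totals from Table 5 are 200, 160, 120, 100, 80, 60 and 40 mg for Levels 1 to -5. Drop one level, give the new total once weekly, and divide by 70 for the BSA below which the cap is exceeded:

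| From level | To level | Single weekly dose | Cap exceeded below | Listed one-day option? |
|---|---|---|---|---|
| 1 | 0 | 160 mg | 160/70 = 2.29 m² | No |
| -1 | -2 | 100 mg | 100/70 = 1.43 m² | Yes |
| -2 | -3 | 80 mg | 80/70 = 1.14 m² | Yes |
| -3 | -4 | 60 mg | 60/70 = 0.86 m² | Yes |
| -4 | -5 | 40 mg | 40/70 = 0.57 m² | Yes |

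The rule gives a listed one-day dose from every level except Level 1.

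**3. How large is the excess?** The protocol equates 80 mg with 45 mg/m², implying a reference BSA of 80/45 = 1.78 m². At 160 mg:

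- 1.43 m² (smallest BSA at which 100 mg respects the cap): 160/1.429 = 112 mg/m²
- 1.78 m²: 160/1.778 = 90 mg/m²
- 2.0 m²: 160/2.0 = 80 mg/m²
- 2.2 m²: 160/2.2 = 72.7 mg/m²

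**4. Comparison with Dose Level 0.** For the same event, the starting-dose patient goes from 160 to 100 mg a week (60/160 = 37.5% less). The escalated patient goes from 200 to 160 mg a week (40/200 = 20% less), and the single dose rises from 100 to 160 mg.

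**The case against.** The strongest reply is that part of the text cannot be seen. A redaction closes each of the three rows, and others follow the BSA text in Sections 11.1.3 and 11.1.5.5. An instruction for Dose Level 1 could sit in any of them. This stands as a real uncertainty and makes the point conditional, but the visible instruction still says what it says.

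Second, the cap is absolute, Table 6 is titled as guidelines, Table 5 lists no one-day option at Dose Level 0, and the Medical Monitor should be consulted first. A careful reader would conclude that the cap wins. That also stands: it makes a 160 mg dose less likely in practice. But these safeguards contradict the row without correcting it, and they work only if someone notices the conflict.

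Third, exposure is narrow: a patient must be escalated and then develop Grade 3 or worse thrombocytopenia while at 100 mg twice weekly. This is accepted.

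Some stronger readings are tempting but not supported:

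- *A larger single dose after toxicity is itself an error.* Moving from 80 mg twice weekly to 100 mg once weekly is an explicit feature of these rows. The problem is only the conflict with the cap.
- *The second-occurrence note produces a further forbidden dose of 120 mg.* In the Grade 3 and Grade 4 rows without bleeding, that note says "or baseline and resume at 1 dose level lower dosed at QW schedule" and does not mention the weekly total. Even read that way, 120/1.778 = 67.5 mg/m² is within the cap at the reference BSA.
- *The dose also breaks a general 100 mg maximum in the SAP.* SAP Section 1.1 gives that figure as a limit on the escalation step, not as a rule for dose reductions.

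**Conclusion.** The conflict is real on the visible text. For a patient at Dose Level 1, all three thrombocytopenia rows lead to a single 160 mg dose. This is over the 70 mg/m² cap at BSA below 2.29 m², reaches 90 mg/m² at the protocol's reference BSA, and is not a one-day option in Table 5. The pattern in the other levels suggests that Dose Level 1 was overlooked when the branches were written.

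The conclusion rests on two assumptions: that the redacted text does not already deal with Dose Level 1, and that the cap applies per administration, as Section 5.1 implies.

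A reader might infer that patients received 160 mg. The documents do not show this: they give no count of escalated patients, which is probably small, and the cap prohibits the dose. The point concerns dosing safety and internal consistency. It does not affect the ORR analysis.

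**What to change.** First check the redacted text in the three rows. If it already directs Dose Level 1 elsewhere or applies the cap, no change is needed.

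Otherwise amend Table 6 as follows:

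- In all three rows, extend the first branch to cover patients on Dose Level 0 or Dose Level 1, so that both go to Dose Level -2 given as 100 mg once weekly. That dose is listed in Table 5 and is within the cap at BSA of 1.43 m² or more, essentially the BSA already required for escalation.
- Add one sentence stating that no single once-weekly dose may exceed 70 mg/m². This also covers a Dose Level 0 patient with BSA below 1.43 m², who has not passed the escalation check.

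Protocol Section 14.5 requires a written amendment with ethics approval, and health authority approval where required, so a letter to sites would not be enough. It needs no extra patients, assessments or analyses.

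The clinical cost is that the escalated patient's weekly dose falls from 200 to 100 mg (50%) instead of 200 to 160 mg (20%). The medical team may prefer another dose, provided it stays within the cap.

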### 9.4.3. Clinical Laboratory Assessments

The following clinical laboratory tests should be performed as indicated in [Table 1](#).

- Hematology (blood sample: ethylenediaminetetraacetic acid [EDTA]) tests including hemoglobin, hematocrit, mean corpuscular volume, mean corpuscular hemoglobin, mean corpuscular hemoglobin concentration, white blood cell (WBC) count, WBC differential, red blood cell count, lymphocytes, monocytes, neutrophils, eosinophils, basophils, and platelets. WBC differential may be automated or manual as per institutional standards.

- Serum Chemistry (blood sample: serum)
  - Complete Serum Chemistry will include sodium, potassium, chloride, bicarbonate ( $\text{HCO}_3^-$ ), blood urea nitrogen (BUN), creatinine, glucose, calcium, phosphate, magnesium, ALT, AST, alkaline phosphatase, LDH, total protein, albumin, amylase, lipase, creatine kinase and uric acid.
  - Limited Serum Chemistry will include sodium, potassium, chloride, bicarbonate, BUN, creatinine, glucose, ALT, AST, alkaline phosphatase, total bilirubin and LDH, unless otherwise clinically indicated.
  - Thyroid-stimulating hormone (TSH)
- Coagulation parameters will include prothrombin time (PT), international normalization ratio (INR), and activated partial thromboplastin time (aPTT).
- Urinalysis will include appearance, color, urine bilirubin, glucose, hemoglobin, ketones, pH, protein, specific gravity, and urobilinogen. Microscopy will only be performed if clinically indicated.

Blood chemistry will be analyzed at each study site by a certified local laboratory and a report of the laboratory values will be provided to the Investigator. The Investigator or designee will review the laboratory results and assess the clinical significance of all abnormal values. Appropriate action will be taken for any clinically significant abnormal values. Values will be documented on the laboratory report until stabilized, or the laboratory value returns to a clinically acceptable range (regardless of relationship to study medication) or baseline. Any laboratory value that remains abnormal at the EoT Visit and that is considered clinically significant will be followed according to accepted medical standards for up to 30 days or until resolution of the abnormality or return to baseline. Toxicity will be assessed using CTCAE version 4.03.

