#### **12.1.1. AE and SAE Follow-up**

All AEs occurring during the study are to be followed up in accordance with good medical practice until they are resolved, stabilized or judged no longer clinically significant or, if a chronic condition, until fully characterized. Any AEs that are considered drug-related must be followed until resolution or until stabilization.

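### Protocol Table 6, Grade ≥3 thrombocytopenia with bleeding: the Day 1 note lets a cycle open and weekly platelet checks stop at Grade ≤3, short of the same row's restart threshold of Grade ≤2 or baseline

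*Protocol*

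**What the plan says.** In Protocol Table 6, the row for Grade ≥3 thrombocytopenia with bleeding first holds dosing until the bleeding is over and the patient is stable. That sentence names no platelet grade. The restart paragraphs do. For a patient on the starting dose, the restart comes on recovery to Grade ≤2 "or baseline, dose reduce to 100 mg total dose per week (Dose Level -2) but dosed at the QW schedule". For all other dose levels the platelet condition is the same and the dose falls by one level.

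The row ends with a note for events on Day 1 of a cycle. The cycle start is delayed and the site is to "check platelet counts weekly until the bleeding has stopped, recovery to Grade" ≤3, and until "the patient is clinically stable and follow the guidelines above".

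Two neighbouring rows also carry Day 1 notes:

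- **Grade 4 without bleeding.** The first restart is at Grade ≤3. For a "second occurrence or worsening thrombocytopenia despite measures above: Hold selinexor until recovery to Grade" ≤2 or baseline. The Day 1 note, for every occurrence, says to "delay the start of the cycle and check platelet counts weekly until recovery to Grade" ≤3.
- **Neutropenia, Grade 3 or 4.** The restart is at Grade ≤2 or baseline, and the Day 1 note says to "delay start of a cycle and check neutrophils weekly until recovery to Grade" ≤2 or baseline, with the other conditions repeated.

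**The concern.** The weekly checks exist to show when it is safe to go on after a bleed. In this row they may end at a platelet level at which selinexor may not yet be given. For a Grade 3 event the note's platelet condition is already met at onset, so it asks for no platelet recovery. Only the other two conditions, bleeding stopped and patient stable, keep the delay and the checks going.

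There are two consequences. A site may open the cycle and stop weekly counts while the patient is still at Grade 3 and still waiting to restart. Or a site may take the end of the delay as permission to dose. Both concern patient safety and consistent conduct across sites. Neither touches the primary analysis.

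**Working it through.** There is no planned figure to reproduce. The check sets the thresholds side by side and then sizes the group affected.

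**Thresholds in Protocol Table 6**

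| Row | Platelets or neutrophils needed to restart | Day 1 note ends at | Agree? |
|---|---|---|---|
| Thrombocytopenia Grade ≥3 with bleeding | Grade ≤2 or baseline, every dose level | Grade ≤3 | No |
| Thrombocytopenia Grade 4 without bleeding, first occurrence | Grade ≤3 | Grade ≤3 | Yes |
| Same row, second or worsening occurrence | Grade ≤2 or baseline | Grade ≤3 | No |
| Neutropenia Grade 3 or 4 | Grade ≤2 or baseline | Grade ≤2 or baseline | Yes |

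The bleeding note uses the Grade 4 note's threshold, which fits a first occurrence there but not here. A carry-over is plausible, though the documents do not say so.

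**Where the thresholds differ.** SAP Table 7-2 puts Grade 3 at 25 to below 50 ×10⁹/L. That is the gap between Grade ≤3 and Grade ≤2.

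**Does the baseline alternative close the gap?** Only for a patient whose own baseline is below 50 ×10⁹/L. Protocol 8.4, criterion 12, requires at least 50,000/mm³ within 21 days before Cycle 1 Day 1. A lower value on Day 1 itself, or a sponsor waiver (Protocol 13.2.1.1), could produce such a baseline. The definitions in Protocol 13.3.7.2 and SAP 2.5 that point to the Day 1 value are written for analysis, not dosing. For most patients the gap stays open.

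**What counts remain once weekly checks end?** Protocol Table 1 schedules the CBC on Cycle 1 Day 15, Cycle 2 Days 1 and 15, and Day 1 of each later cycle. If a delayed Cycle 2 opens at Grade 3, the next scheduled count is 15 − 1 = 14 days later. From Cycle 3 it is at the next Day 1, 28 days later (window ±2 days).

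**How many patients?** Protocol 4.3.1.4 reports one clinically significant thrombocytopenia-related bleed among 92 patients (cut-off 31 March 2017).

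- Rate: 1/92 = 0.0109.
- Exact 95% limits: lower 1 − 0.975^(1/92) = 0.00028. The upper limit solves (1−p)⁹² + 92p(1−p)⁹¹ = 0.025, giving p = 0.0591.
- Scaled to about 130 Part 2 patients: 130 × 0.0109 = 1.41 (0.04 to 7.68).
- The share s found on Day 1 is not given, so it is assumed. With s = 1/28 (events even over the cycle), 1.41/28 = 0.05 (0.001 to 0.27). With s = 0.5, 0.71 (0.02 to 3.84). With s = 1 (all found at the Day 1 visit), 1.41 (0.04 to 7.68).

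For the second-or-worsening branch of the Grade 4 row there is only a ceiling. Grade 3/4 treatment-related thrombocytopenia occurred in 51% of 92, and 0.51 × 130 ≈ 66. This pools Grade 3 with Grade 4, all occurrences and all days, so it says almost nothing about that branch.

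**The case against.** The strongest reply is that restart is not in doubt. The row prints Grade ≤2 or baseline for every dose level, and the note closes by returning the reader to it. That stands. A reader might infer that the note tells sites to dose at Grade 3. Read in full, it does not.

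A reader might also infer that a Grade 3 event satisfies the whole note at onset. It satisfies only the platelet part, because bleeding must also have stopped and the patient must be stable.

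Nor is it right that nothing else sets an interval. Table 1 schedules counts, and a site applying the restart rule has to measure platelets to know that it is met. For events on other days the row sets no weekly checks at all, so the note adds monitoring. Protocol 11.1.1 asks for Medical Monitor discussion of dosing changes. Protocol 11.1.5 takes a patient off treatment if drug-related toxicity delays it by more than 28 days. Protocol 12.1.1 adds "Any AEs that are considered drug-related must be followed until resolution or until stabilization", and 9.4.3 says "Values will be documented on the laboratory report until stabilized, or the laboratory value returns to a clinically acceptable range". These lower the risk. But the two follow-up clauses set no count interval or restart grade, and from Cycle 3 the Table 1 schedule does not replace weekly checks.

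Even the worst misreading has limited effect. For a first Grade 3 event without bleeding, Table 6 does not hold selinexor but reduces it, from the starting dose, to 100 mg once weekly. That is also the restart dose after a bleed. This too stands, although the row plainly means to be stricter after a bleed.

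Finally, redacted text follows the note and could hold a clarification. The point is confined to what is visible.

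**Conclusion.** The point holds as a minor internal inconsistency in a safety rule. On visible text, the note's end point for the cycle delay and weekly checks is looser than the row's own restart threshold, and the gap is 25 to below 50 ×10⁹/L. The documents support neither an instruction to dose at Grade 3 nor a complete absence of monitoring. What remains is that weekly checks can stop too early and that the note can be misread.

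The expected number is small, from 0.05 to 1.4 of 130 patients. This rests on one event in 92, on an assumed Day 1 share between 1/28 and 1, and on carrying that rate over to Part 2. The platelet grade and day of the one bleed are not reported. In Protocol Table 3, 51 of 78 patients received 6 rather than 8 doses per cycle, so the Part 2 rate may differ. The row also covers bleeds that are not clinically significant, so the count could be higher. The ORR test is unaffected.

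The second-or-worsening branch of the Grade 4 row is a secondary consistency point. That rule stands above its Day 1 note and is among the guidelines to which the note refers.

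**What to change.** In the bleeding row's Day 1 note, replace Grade ≤3 with Grade ≤2 or baseline, and keep the two other conditions (bleeding stopped, patient clinically stable). The delay and the weekly checks then end at the level at which selinexor may restart, as in the neutropenia row.

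For consistency, let the Day 1 note for Grade 4 without bleeding use Grade ≤2 or baseline for second or worsening occurrences only, and leave Grade ≤3 for the first. The clinical team should confirm both thresholds and check them against the redacted text.

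The cost is a few words of protocol text. Some Day 1 cycle starts would be slightly later and a few more weekly counts would be taken. No analysis changes.
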